4.3.8 V8: Safety follow-up visit (Week 16 (Day 112) \pm 3 days)

V8 is a telephone follow-up visit to inquire about the occurrence of AEs, and collecting information on concomitant medication and non-drug treatment; if the subject has abnormal results in previous laboratory tests or other tests, the investigator may arrange the subject to receive the test or examination again in the hospital based on the clinical judgment.

4.3.9 Pre-salvage therapy visit

Investigators should give the subjects the central laboratory test again for FPG within 7 days of being informed that the subject's test results have reached the hyperglycemia threshold for salvage therapy (see Section 3.3.2). Subjects whose central laboratory test results meet the hyperglycemia threshold for salvage therapy will receive the pre-salvage therapy visit before the salvage therapy. If the time point between the pre-salvage therapy visits and the follow-up routine visit (V5 or V6) in the double-blind treatment phase is ≤ 7 days, the follow-up routine treatment visit (V5 or V6)

is not required. If the subject has contraindications to salvage therapy, the pre-salvage therapy visit is not required, and the subject should withdraw from the study early and receive the withdrawal visit.

Protocol No.: HTD1801.PCT103

The subject should arrive at the study site under the fasting condition. The blood samples should be collected under the fasting condition. It is recommended to collect the fasting blood samples at $7:00 \sim 10:00$ a.m. Procedures to be completed at this visit include:

- Body weight;
- Clinical laboratory tests (blood biochemistry, hematology, urinalysis; the specific items included are shown in APPENDIX 7);
- PPK blood sample collection (within 1 hour before dosing);
- HbA1c;
- Fasting blood glucose, fasting insulin, fasting C-peptide;
- Liver function and blood lipid test (LDL-C, HDL-C, TG, TC, AST, ALT, GGT, TBIL, fasting);
- C-reactive protein (fasting);
- Intestinal flora metabolomics serum samples (fasting);
- 12-lead ECG;
- Liver transient elastography;
- Feces collection (if any);
- Guidance on lifestyle;
- Distributing the drug for salvage therapy;
- Recording concomitant medications or treatments;
- Recording AEs.

4.3.10 Salvage therapy evaluation visit (4 weeks after salvage therapy \pm 3 days)

If the subject has received salvage therapy for 4 weeks during the 12-week double-blind treatment phase, a salvage therapy evaluation visit is required to evaluate the effect of salvage therapy by FPG; if the salvage therapy evaluation visit time (including the visit window) coincides with the routine visit time (including the visit window) during the double-blind treatment phase, they will be pooled into one visit, and the content of the visit should meet the requirements of both visits; the effect of salvage therapy will be evaluated according to FPG. If the subject's FPG does not reach the corresponding hyperglycemia threshold set in the protocol, it is defined as success in salvage therapy, and the subject will continue to use salvage therapy drugs in addition to the investigational drug according to the protocol. If the subject's FPG reaches the corresponding hyperglycemia threshold set in the protocol, it is defined as failure in salvage therapy, and the subject will withdraw from the study, and the reasons for withdrawal are recorded as "Failure in Salvage Therapy". If the subject is receiving salvage therapy at the end of the 12-week double-blind treatment phase, but the salvage therapy duration was less than 4 weeks, the salvage therapy evaluation visit is not required, and the V7 visit is carried out according to the normal procedure.

The subject should arrive at the study site under the fasting condition. The blood samples should be collected under the fasting condition. It is recommended to collect the fasting blood samples at $7:00 \sim 10:00$ a.m. Procedures to be completed at this visit include:

- Physical examination;
- Vital signs;
- Clinical laboratory tests (blood biochemistry, hematology, urinalysis; the specific items included are shown in APPENDIX 7);

Protocol No.: HTD1801.PCT103

- Fasting blood glucose;
- 12-lead ECG;
- Guidance on lifestyle;
- Distributing the drug for salvage therapy;
- Recording concomitant medications or treatments;
- Recording AEs.

4.3.11 Unscheduled visits

Unscheduled visits may be given based on clinical needs. The contents and results of unscheduled visits should be recorded. For all subjects in the Phase II study, efficacy assessments and recordings should be performed according to the visits planned in the study schedule.

5. INVESTIGATIONAL DRUG

5.1 General Information on Drugs

5.1.1 Study products

Investigational Drug

Drug name: HTD1801 Capsules

Dosage form: capsule

Strength: 250 mg/capsule

Appearance: yellow capsule

Expiry date: 18 months (it is tentative and will be revised based on the accumulated data on

Protocol No.: HTD1801.PCT103

stability studies)

Storage conditions: stored in a tight container at room temperature.

Supplier: Shenzhen HighTide Biopharmaceutical, Ltd.

Manufacturer: the drug was provided by Shenzhen HighTide Biopharmaceutical, Ltd., and manufactured by the contract manufacturing organization Shanghai STA Pharmaceutical Product Co., Ltd.

Control Drug

Drug name: HTD1801 Placebo Capsules

Dosage form: capsule

Strength: the capsules correspond to the investigational drug strength, but do not contain any active pharmaceutical ingredient.

Appearance: yellow capsules with the same appearance, color and smell as the investigational drug

Expiry date: 18 months (it is tentative and will be revised based on the accumulated data on stability studies)

Storage conditions: Stored in a tight container at room temperature.

Supplier: Shenzhen HighTide Biopharmaceutical, Ltd.

Manufacturer: the drug was provided by Shenzhen HighTide Biopharmaceutical, Ltd., and manufactured by the contract manufacturing organization Shanghai STA Pharmaceutical Product Co., Ltd..

5.1.2 Drug for salvage therapy

Drug name: Empagliflozin

Dosage form: tablets

Strength: 10 mg/tablet

Supplier: Shenzhen HighTide Biopharmaceutical, Ltd.

Storage condition: stored in a well-closed container (according to the instructions for use)

5.1.3 Route of administration

5.1.3.1 Usage and dosage of the investigational drug for the single-blind introduction period:

The placebo should be taken with meals, 4 capsules, BID.

5.1.3.2 Usage and dosage of the investigational drug for the double-blind treatment phase:

Protocol No.: HTD1801.PCT103

500 mg BID dose group: 2 HTD1801 capsules (250 mg/capsule) + 2 placebo capsules should be taken with meals (in the standard meal process on the days of V6 and V7: the drug should be taken immediately after the first bite); the dosing frequency should be BID throughout the double-blind treatment phase, except for QD in the evening on the day of V4 (Day 1), and QD in the morning on the day of V7 (Day 84).

1000 mg BID dose group: 4 HTD1801 capsules (250 mg/capsule) should be taken with meals (in the standard meal process on the days of V6 and V7: the drug should be taken immediately after the first bite); the dosing frequency should be BID throughout the double-blind treatment phase, except for QD in the evening on the day of V4 (Day 1), and QD in the morning on the day of V7 (Day 84).

Placebo group: 4 placebo capsules should be taken with meals (in the standard meal process on the days of V6 and V7: the drug should be taken immediately after the first bite); the dosing frequency should be BID throughout the double-blind treatment phase, except for QD in the evening on the day of V4 (Day 1), and QD in the morning on the day of V7 (Day 84).

5.1.3.3 Salvage therapy

If the subject meets the criteria for initiating the salvage therapy (see Section 3.3.2.1), the salvage therapy should be initiated with Empagliflozin. On the basis of treatment with the investigational drug, the investigator will determine the usage and dosage of Empagliflozin according to the conditions of the subjects, and referring to the instructions for use of Empagliflozin and Diagnosis and Treatment Guidelines for Diabetes Mellitus.

5.2 Drug Packaging and Label

Packaging and labeling of all investigational drugs were performed by Shenzhen HighTide Biopharmaceutical, Ltd. and contract research organizations (CROs) in accordance with terms and applicable national regulations of the Good Clinical Practice (GCP).

The drug label should at least include the following: protocol number, drug number, randomization number, drug strength, drug batch number, expiry date, packaging specification, usage and dosage, storage conditions, and Sponsor name. The label must state "for clinical study use only, please keep out of reach of children".

5.3 Drug Dispensing, Inventory and Return

The investigational drug used in this study should be provided and handled in accordance with GCPs. The investigational drug-related drugs should be handled by the drug administrators authorized by the clinical study site, including receipt, inventory management, medication, drug recovery, and maintenance related records of each subject. The drug administrators or investigators of the study site should store enough investigational drugs according to the Sponsor's recommendation and distribute them to the subjects. The investigational drug must be distributed as required by the protocol. The investigational drugs are provided free of charge by the Sponsor, and distributed to each study site as scheduled. Special personnel assigned by the clinical study site are responsible for preserving and distributing the drugs.

Investigators and/or drug administrators must record the distribution and return information of all investigational drugs in a timely manner on the drug distribution records, and can distinguish each subject by the random number. The number of drugs dispensed and returned for each subject, the drug number, and the corresponding visit date are recorded in the form. The inventory form is updated synchronously by drug administrators and/or investigators, recording (with dates of receipt or dispensing) incoming, outgoing, and inventory. After the subjects complete the placebo introduction period and are determine to meet the eligibility criteria, eligible subjects will be randomized, and the investigators and/or drug administrators will distribute the drug to the subjects according to the drug numbers assigned by the IWRS. In addition, the investigators and/or drug administrators will inform subjects to return used empty boxes and/or drug packaging bags and/or unused drugs to drug administrators at each follow-up visit.

Protocol No.: HTD1801.PCT103

During the study, the investigators should track the subjects' medication to ensure that the subjects take the investigational drugs properly; and remind the subjects to pay attention to the storage conditions of the drugs. During the study, the investigator should record the number of drugs used by the subjects in detail to determine the medication compliance of the subjects, which is conducive to the correct judgment of the efficacy and safety of the drug. The monitors should count the drugs during the inspection, and the investigational drugs should be used properly. After the drugs are counted during the visit, the drug loss should be recorded in detail in the drug distribution records, and the overdose, missed dose and drug loss should be recorded in the eCRF.

At the end of study, the investigational drug delivery records must be the same as the quantities used and destroyed/returned. Any discrepancies should be recorded and the reason for the discrepancy should be noted.

5.4 Missed Dose

While the subjects are at home, each medication should be recorded in the subject diary, and the subject diary and remaining drugs should be submitted at the follow-up visit for the investigator to review the subject diary and count the remaining quantity and empty packaging of the investigational drug.

In the event of a missed dose, the following rules apply:

- If the missed drug is within 6 h (including 6 h) of the time interval for administration, the investigational drug should be supplemented according to the dose immediately;
- If the missed drug is 6 h out of the time interval for administration, there is no need to supplement the investigational drug;
- Follow-up administration time will be not affected by supplemented administration of the investigational drug.

6. CONCOMITANT/PROHIBITED MEDICATIONS AND TREATMENT

6.1 Concomitant Medication

6.1.1 Allowed concomitant medications/treatment:

Without the consent of the investigator, no other hypoglycemic drugs other than the investigational drug can be used throughout the study, except for the drugs used for the treatment of AEs. Concomitant drugs (such as antihypertensive, lipid-lowering drugs) before the study should continue to be used at their original doses, and the reasons for their use should be fully recorded in the eCRF. Any new concomitant medications/treatments, or changes in concomitant medication doses, and the reason for medication, dates of administration (including start and end dates), and dosing information (including dose, route, frequency) must be recorded in the corresponding section in the eCRF from the signing of the ICFs through the entire treatment phase and during the safety follow-up visit.

Protocol No.: HTD1801.PCT103

6.1.2 Prohibited concomitant medications/treatment:

The following limitations on prohibited concomitant treatments or drugs do not apply to the salvage therapy administered to subjects by the investigator according to the protocol (see Section 5.1.3.3). During the period from the subject signs the ICFs to the end of the double-blind phase (excluding the safety follow-up visit phase and early withdrawal visit), the prohibited concomitant treatments include:

- Any drugs that may affect blood glucose metabolism, such as:
- Hypoglycemic drugs (including traditional Chinese medicines indicated for hypoglycemic therapy)
- Systemic glucocorticoids (except inhalation, eye instillation, and topical dermal application)
- Growth hormone
- Non-selective β-receptor blockers (such as propranolol, etc.)
- Thiazide diuretics at a dose > 25 mg/day
- Aspirin at a dose >300 mg/day
- Thyroid hormones: During the study, no new thyroid hormone drugs or changes in the previous drug regimen (except stable replacement therapy) are allowed.
- Liver-protecting drugs (including traditional Chinese medicine) or dietary supplements (see APPENDIX 1)
- Any chemical drugs, traditional Chinese medicines or dietary supplements for weight loss (see APPENDIX 2), a weight loss program, or a special diet.
- robiotic-containing drugs or dietary supplements (see APPENDIX 3).
- New use of drugs for controlling blood lipid and blood pressure, or changes in previous drug regimens
- Blood transfusion or use of blood products is required.
- Vaccines (except for inactivated vaccines).
- Drugs or treatments that, in the judgment of investigators, may affect the objectivity of the assessment of safety and/or efficacy of subjects in this study.

• Traditional Chinese Medicine.

Unless in emergencies, subjects are prohibited from using any new drug that is not reported during the screening phase without prior consultation with the investigator or self-adjusting the dose of concomitant drugs during the study. In emergencies, if there is a clinical indication for the use of a new drug or dose modification of the concomitant drug, the subject must notify the investigator before using the concomitant drug. The investigator will determine and record any emergency medication's usage, name, dose, route of administration, objectives of treatment, and date of administration.

Protocol No.: HTD1801.PCT103

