3.3.1.2 Principles for withdrawal due to hypoglycemia

If the subject experiences 1 Grade 3 hypoglycemia during the double-blind treatment phase, and there are no other major causes for hypoglycemia (for example, increased physical activity or missed meals, etc.) other than the investigational drug, then the investigational drug should be discontinued, and the subject will withdraw from this study. The cause for withdrawal should be recorded as "withdrawal due to hypoglycemia", and other anti-diabetic drug treatment will be given by the investigator in accordance with clinical practice.

If the subject experiences 2 < Grade 3 hypoglycemia during the double-blind treatment phase, and there are no other major causes for hypoglycemia (for example, increased physical activity or missed meals, etc.) other than the investigational drug, then the investigational drug should be discontinued, and the subject will withdraw from this study. The cause for withdrawal should be recorded as "withdrawal due to hypoglycemia", and other anti-diabetic drug treatment will be given by the investigator in accordance with clinical practice and in compliance with the requirements of the protocol.

If the subject experiences 1 Grade 3 hypoglycemia during the salvage therapy (see Section 5.1.3.3), and there are no other major causes for hypoglycemia (for example, increased physical activity or missed meals, etc.) other than the investigational drug and the salvage therapy drug, then the investigational drug and the salvage therapy drug should be discontinued, and the subject will withdraw from this study. The cause for withdrawal should be recorded as "withdrawal due to hypoglycemia", and other anti-diabetic drug treatment will be given by the investigator in accordance with clinical practice and in accordance with the requirements of the protocol.

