3.3.2.2 Principles for withdrawal due to failure in hyperglycemia salvage therapy

During the double-blind treatment, when the FPG test result of the subject or the fingertip blood glucose measurement recorded in the subject diary reaches the hyperglycemia threshold for salvage therapy, the investigator should, after learning the results, confirm that subject's poor blood glucose control is caused by the following:

- 1) The subject fails to adhere to the diabetic diet and exercise lifestyle;
- 2) The subject has a concurrent disease that may affect blood glucose control;
- 3) The subject has poor compliance, and dose not take the investigational drug as required.

If the above factors are not present, the investigators should give the subjects the central laboratory test again for FPG within 7 days of being informed of the test results.

If the above factors exist, the investigators should take appropriate measures (such as providing relevant training and education for the subjects), and give the subject a central laboratory test of FPG within 7 days.

Based on the central laboratory FPG results, when the investigator determines that salvage therapy is required, the usage and dosage of the salvage drug (Empagliflozin) will be determined with reference to the Instructions for Use of the drug and diagnosis and treatment guidelines for diabetes mellitus.

Subjects should receive the pre-salvage therapy visit before the salvage therapy. If the subject has contraindications to the salvage therapy, the investigator will arrange the subject to withdraw from the study and conduct a withdrawal visit, and the reason for withdrawal is recorded as "failure to Study Protocol: Version 2.0/Date: 4/27/2022 Confidential Page 41

receive the hyperglycemia salvage therapy".

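### Section 6.1.1 can be read as allowing other glucose-lowering drugs during double-blind treatment that Section 6.1.2 prohibits; separately, the on-treatment estimand rows keep post-salvage data

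*Protocol*

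**What the plan says.** Section 6.1.1, headed as allowed medication, says: "Without the consent of the investigator, no other hypoglycemic drugs other than the investigational drug can be used throughout the study". It adds an exception: "except for the drugs used for the treatment of AEs". Neither clause is limited to a study phase or tied to salvage.

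Section 6.1.2 lists hypoglycemic drugs as prohibited from signature of the consent form "to the end of the double-blind phase (excluding the safety follow-up visit phase and early withdrawal visit"). It says that its limits "do not apply to the salvage therapy administered to subjects by the investigator according to the protocol", with a reference to Section 5.1.3.3. Its closing paragraph allows for new drugs in emergencies: the subject must notify the investigator, who determines and records the drug. That paragraph does not mention hypoglycemic drugs.

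Other sections bear on which rule is meant:

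- Section 5.1.3.3: "the salvage therapy should be initiated with Empagliflozin".
- Section 3.3.2.2: "If the subject has contraindications to the salvage therapy, the investigator will arrange the subject to withdraw from the study".
- Section 3.3.1.2, on withdrawal for hypoglycemia: "other anti-diabetic drug treatment will be given by the investigator in accordance with clinical practice".
- Study Process, note 3: the investigator may give other antidiabetic drugs during safety follow-up.

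On analysis, Section 10.3 requires that per-protocol subjects have no serious protocol violations. Section 10.4.3 makes what the protocol calls the therapy strategy (read here as treatment policy) the main approach, with the on-treatment strategy as sensitivity analysis. The estimand table in Section 10.4.4 sets out both strategies for salvage.

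**The concern.** The drugs in question lower HbA1c, whose change from baseline over 12 weeks is the primary endpoint. If an investigator agrees to add a second agent in Week 5, one site can point to 6.1.1 and regard this as permitted. Another can point to 6.1.2 and record a violation. Two things are then at stake: sites may treat comparable subjects differently, and per-protocol membership of such a subject depends on which section is applied.

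A natural remedy is to handle any such drug as salvage is handled. The salvage handling has an error of its own, however: the on-treatment rows of the estimand table do not do what an on-treatment strategy is there to do.

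**Working it through.** No sample size, power or alpha figure is involved, so the check is a comparison of texts.

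**Step 1: Sections 6.1.1 and 6.1.2 by situation**

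| Situation | 6.1.1 | 6.1.2 | Result |
|---|---|---|---|
| Empagliflozin salvage, double-blind phase | Not named; fits under investigator consent | Expressly exempt | Compatible |
| Another glucose-lowering agent, double-blind phase, investigator agrees | Not barred by the wording | Prohibited | Differ if consent is taken as enough |
| Glucose-lowering drug given for an adverse event, double-blind phase | Excepted | No express exemption; emergency paragraph does not say the list is lifted | Unclear |
| Another agent after withdrawal or in safety follow-up | Possible with consent | Outside the prohibition | Compatible |

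The second and third rows need repair.

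**Step 2: which rule is intended**

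Section 5.1.3.3 names a single salvage drug. Section 3.3.2.2 withdraws a subject who cannot take it and does not offer a substitute. Section 3.3.1.2 and Study Process note 3 place other antidiabetic drugs after withdrawal or in follow-up. All of this agrees with 6.1.2, so 6.1.1 is the text to change.

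**Step 3: where the effect can fall**

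Sustained hyperglycemia already has its own route in Section 3.3.2: threshold, central-laboratory retest, empagliflozin, and withdrawal on failure. Unclear cases are therefore mainly short or emergency use, or an investigator who relies on 6.1.1 to add a drug outside that route. The main efficacy analysis uses the FAS under treatment policy, which would most naturally keep the data. The PPS is where status becomes unclear.

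**Step 4: the estimand table, Section 10.4.4**

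| Endpoint block | Treatment-policy row, post-salvage data | On-treatment row, post-salvage data |
|---|---|---|
| Primary (HbA1c change) | Included | Included |
| Secondary, continuous | Included | Included |
| Secondary, categorical | Included | Apparently included (row garbled in the text available) |

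In both fully legible blocks the two strategies give the same instruction. An on-treatment analysis offered as a sensitivity analysis to treatment policy should set aside data after salvage starts. As written, it cannot differ on that point.

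**The case against.** The best defense is that the consent clause in 6.1.1 states a necessary condition and not a sufficient one. It says what may not happen without consent; it does not say that consent opens the door to any agent at any time. It also covers the whole study, including salvage and safety follow-up, where investigator-chosen treatment is legitimate. Section 6.1.2 is then the narrower rule for a defined period, and a specific rule normally governs. This reading is fair, and it is why the point is worded as what 6.1.1 can be read to allow. It does not settle the matter, because the clause stands under a heading of allowed medication and does not mention salvage or phase.

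A reader might go further and infer that the adverse-event exception contradicts 6.1.2 however it is read. The protocol does not support that. The emergency paragraph closing 6.1.2 is a partial counterpart, and the exception may be a loosely translated carve-out for adverse-event treatment in general. What remains is that the paragraph does not say whether the prohibited list yields.

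It is also fair to say that the estimand-table error is a separate matter. Section 6.1.1 can be reworded without touching it, and it adds no weight to the conflict between 6.1.1 and 6.1.2. It is reported here because the same amendment can correct it.

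**Conclusion.** The point holds as a minor inconsistency. As worded, 6.1.1 leaves room for added glucose-lowering drugs that 6.1.2 prohibits during double-blind treatment, and the rest of the protocol supports 6.1.2. The consequence is limited to inconsistent site practice and unclear per-protocol status for any subject concerned. A reader might infer a biased primary result. The protocol gives no expected frequency of such use and no effect size for it, so neither bias nor loss of power can be claimed or calculated.

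The on-treatment rows are wrong as written for the primary and continuous secondary endpoints, and apparently for the categorical ones. This rests on the assumption that the on-treatment strategy was meant to set aside post-salvage data, which its role in Section 10.4.3 supports. The sensitivity analysis may still differ from the main analysis in other respects; the finding concerns post-salvage data only.

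**What to change.** 1. Reword 6.1.1: during double-blind treatment the only added glucose-lowering drug is empagliflozin salvage under 5.1.3.3; other agents may be given only after withdrawal or in safety follow-up.
2. In the closing emergency paragraph of 6.1.2, state whether short emergency or adverse-event use is an exception to the prohibited list.
3. In the on-treatment rows of the Section 10.4.4 table, change the handling of post-salvage data from included to excluded. Treat any other added glucose-lowering drug in the same way: kept under treatment policy, excluded from its start in the on-treatment analysis.

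An extra HbA1c sample before such a drug is optional. The withdrawal-visit sample does not serve this purpose for a subject who continues treatment, because that visit applies only to subjects who withdraw. Post-baseline HbA1c is otherwise scheduled at Weeks 8 and 12 and at the pre-salvage visit. A drug started before Week 8 outside the salvage route would therefore leave no on-treatment value without an extra sample.

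The cost is a protocol amendment and the loss of the investigator's discretion to add another agent during treatment. Section 3.3.2.2 already directs withdrawal when empagliflozin is contraindicated. Concomitant medication is already recorded under 6.1.1, so items 1 to 3 need no new visit or case report form field.
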